10.3 Sensitivity Analyses of the Primary Efficacy Analysis

10.3.1 Sensitivity Analysis Assuming Time of Symptom Response of 21 Days for Discontinued Subjects

Repeat the primary efficacy analysis assuming a time of Symptom Response of 21 days (504 hours from first dose of study medication) for subjects who discontinued the study prior to achieving Symptom Response.

Analysis Population(s):	Confirmed Influenza
Derived Variables:	See Section 10.2: Primary Efficacy Analysis.

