8 STATISTICAL CONSIDERATIONS

8.1 Sample Size Calculation

As described in section 7.3 below, the Symptom Response definition for this study will be derived from the subjects' FLU-PRO questionnaire responses. The FLU-PRO-derived endpoint is expected to track very closely to return to usual health status (a daily yes/no question in the FLU-PRO questionnaire). Patient-reported outcomes for time to return to usual health status have been shown to track very closely with time to ability to perform 100% of usual activities.^{27,28,29} We assume, therefore, that the cumulative distributions of time to Symptom Response for the placebo treatment group will closely reflect historical data (Romark studies RM08-3002 and RM08-3003 and oseltamivir studies WV15670 and WV15671) for time from first dose until the subjects report that they are able to perform 100% of usual activities. Based upon data from Romark studies RM08-3001, RM08-3002 and RM08-3003, we assume that treatment with NTZ should result in reduction of at least 40 hours in median time to symptom response with differences being less at the first

quartile and greater at the third quartile. Based upon this historical data, the following curves have been developed for determining sample size.

Based upon these curves, a sample size of 552 subjects with laboratory-confirmed influenza (i.e. 276 for each of the 2 groups) will provide 90% power to detect a statistically significant difference in the survival distributions between NTZ and placebo groups (2-sided alpha of 0.05). This calculation was performed for the Gehan rank test using SAS PROC POWER (SAS 9.4) with the curves shown above (proportion not recovering by the end of each day was used as input) and censoring at day 21 (hour 504). Assuming that 8% of subjects will have incomplete data, we arrive at a sample size of 600 subjects in total, 300 per treatment group to yield at least approximately 550 with complete data (all 600 subjects will be included in the primary analysis with subjects with incomplete data censored as of their last entry).

Based upon these calculations, the study will enroll at least 600 subjects with laboratory-confirmed influenza up to a maximum of 700 subjects with laboratory-confirmed influenza. We estimate that this will require enrollment of 800 to 1,200 subjects in total assuming a flu-positive rate between 50% and 75%.

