- The primary efficacy analysis will be repeated using only items from the four FLU-PRO domains (Body/Systemic, Throat, Chest/Respiratory and Nose) that correspond to the seven symptoms included in the traditional PRO instrument (feverishness, myalgia, headache, fatigue, sore throat, nasal obstruction and cough). For this secondary analysis, we will derive the Symptom Response definition in the same manner as for deriving the Symptom Response definition used in the primary analysis (after removing the Eye and Gastrointestinal symptoms).

Exploratory analyses will be performed as follows:

- For each of the 32 individual FLU-PRO symptoms, Time to Individual Symptom Response for the NTZ and placebo treatment groups will be compared using the Gehan-Wilcoxon test.
- For each of the 6 FLU-PRO domains, Time to FLU-PRO Domain Response for the NTZ and placebo treatment groups will be compared using the Gehan-Wilcoxon test.
- Time to Resolution of Acute Febrile Illness for the NTZ and placebo treatment groups will be compared using the Gehan-Wilcoxon test.
- Time to Return to Usual Health for the NTZ and placebo treatment groups will be compared using the Gehan-Wilcoxon test.
- Changes in influenza TCID₅₀ viral titers from baseline to day 2 and from baseline to day 3 for the NTZ and placebo treatment groups will be compared using a t-test.
- For subjects with laboratory-confirmed influenza, the proportions of subjects with influenza virus detected by culture in nasopharyngeal swabs collected at each of days 2, 3 and 7 will be compared for the two treatment groups using a Fisher's exact test.

Sensitivity analyses for the primary endpoint will include:

- Repeat the primary efficacy analysis, assigning a Time to Symptom Response of 21 days for subjects that discontinue prior to day 21 without achieving Symptom Response.
- Repeat the primary efficacy analysis for a “per protocol” subset.

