⁵ Laboratory safety tests include hemoglobin, hematocrit, complete blood count (total and differential), platelet count, random blood sugar, total cholesterol, HDL, LDL, triglycerides, albumin, AST, ALT, GGT, alkaline phosphatase, bilirubin (total/direct), BUN, creatinine, sodium, potassium, chloride and routine urinalysis (glucose, proteins and blood).

⁶ All subjects will maintain an electronic diary until day 22 (+3). Site staff will contact subjects as needed during study to ensure timely completion of electronic diary.

⁷ Collection of unused IMP and completion of pill count log form will be performed at unscheduled visit if applicable.

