7.3 Sample Size Justification

The Symptom Response definition for this study will be derived from the subjects' FLU-PRO questionnaire responses as described in section 10.2.1 below. The FLU-PRO-derived endpoint is expected to track very closely to return to usual health status (a daily yes/no question in the FLU-PRO questionnaire). Patient-reported outcomes for time to return to usual health status have been shown to track very closely with time to ability to perform 100% of usual activities.^{1,2,3} We assume, therefore, that the cumulative distributions of time to symptom response for the placebo treatment group will closely reflect historical data (Romark studies RM08-3002 and RM08-3003 and oseltamivir studies WV15670 and WV15671) for time from first dose until the subjects report that they are able to perform 100% of usual activities. Based upon data from Romark studies RM08-3001, RM08-3002 and RM08-3003, we assume that treatment with NTZ should result in reduction of at least 40 hours in median time to symptom response with differences being less at the first quartile and greater at the third quartile. Based upon this historical data, the following curves have been developed for determining sample size.

Based upon these curves, a sample size of 552 subjects with laboratory-confirmed influenza (i.e. 276 for each of the 2 groups) will provide 90% power to detect a statistically significant difference in the survival distributions between NTZ and placebo groups (2-sided alpha of 0.05). This calculation was performed for the Gehan rank test using SAS PROC POWER (SAS 9.4) with the curves shown above (proportion not recovering by the end of each day was used as input) and censoring at day 21 (hour 504). Assuming that 8% of subjects will have incomplete data, we arrive at a sample size of 600 subjects in total, 300 per treatment group.

Based upon these calculations, the study will enroll at least 600 subjects with laboratory-confirmed influenza up to a maximum of 700 subjects with laboratory-confirmed influenza. We estimate that this will require enrollment of 800 to 1,200 subjects in total assuming a flu-positive rate between 50% and 75%.

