10.2 Primary Efficacy Analysis: Time to Symptom Response

The primary efficacy analysis will be the comparison of the time from first dose of study medication to symptom response between treatment groups using Kaplan-Meier survival curves and the Gehan-Wilcoxon test stratified by (1) time from onset of illness to time of first dose of study medication (0-24, >24-≤36, or >36 hours from onset), and (2) vaccination status (Y/N).

Definitions:

- Symptom Response The set of criteria to be defined based upon a blinded review of symptom scores (pooled for all influenza-infected subjects without regard to treatment group assignment) that correlate to the time at which subjects report that they return to usual health (a daily global assessment question). Methodology to be used for the derivation of the Symptom Response definition is described in section 10.2.1 below. Symptom scores must be maintained at the defined level for at least 2 daily diary periods without any symptom relief medication during or between those 2 daily diary periods.
- Time of Symptom Response The start of the first daily diary period in which Symptom Response is achieved and is maintained for at least two daily diary periods without any symptom relief medication during or between those two daily diary periods.
- Time to Symptom Response Time (hours) from the first dose of study medication to the Time of Symptom Response.

Variables Used for the Analysis

The primary efficacy analysis will require the following variables:

Variable	Source	Format/Notes
Date and time of first medication intake	CRF	
Date and time of completion for each symptom assessment record	Subject diary	
Symptom score assessment for each symptom for each diary record	Subject diary	The ordinal symptom severity, intensity or frequency score assessment for each of the 32 symptoms will be coded to numerical values 0-4.

Variable	Source	Format/Notes
		
It will not be possible for any individual symptom assessment to be missing within a diary record, therefore no individual item imputation will be required.
 
In the event that the diary was not completed at a specified time point (e.g., Day 2), the missing data will not be imputed.

Date and time of symptom relief medication intake	Sponsor-provided listing	The list of symptom relief medications will be selected from the listing of all concomitant medications prior to unblinding.

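### The 21-day sensitivity analysis is triggered by study discontinuation, so subjects who stop the diary unresolved but stay enrolled are never stress-tested

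*SAP*

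**What the plan says.** - **Primary analysis.** Protocol 8.1 keeps everyone in, with "subjects with incomplete data censored as of their last entry". SAP 10.2.2 does the same: a subject without Symptom Response is censored at the last symptom assessment, whatever the reason. For a missed diary, SAP 10.2 states that "the missing data will not be imputed".
- **Last-diary rule.** Under SAP 10.2.2, a subject who first meets the criteria at the last available diary, with no symptom relief medication in that period, counts as a responder on that single diary.
- **Expected loss.** Protocol 8.1: "Assuming that 8% of subjects will have incomplete data, we arrive at a sample size of 600 subjects in total, 300 per treatment group".
- **Sensitivity analysis for lost outcomes.** SAP 10.3.1 assigns 504 hours "for subjects who discontinued the study prior to achieving Symptom Response". Protocol 8.4.1 describes it as "assigning a Time to Symptom Response of 21 days for subjects that discontinue prior to day 21 without achieving Symptom Response".
- **Second sensitivity analysis.** SAP 10.3.2 repeats the primary analysis in the Per Protocol population. Its definition in SAP 8.1 turns on major deviations and has no diary-completeness criterion.
- **What discontinuation means.** SAP 9.1.1 tabulates subjects as completed or discontinued from the study, and SAP 9.2 lists a date and reason for each discontinuation. Stopping the diary is not among the reasons in Protocol 11.2. Under Protocol 5.3, a missing diary leads site staff to contact the subject.

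**The concern.** The outcome is lost when the diary stops, but 10.3.1 acts only when the subject leaves the study. Two subjects can have identical diaries ending on Day 5 with symptoms unresolved. If one withdraws and the other stays enrolled and attends Day 22, the first is moved to 504 hours and the second remains censored at Day 5.

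Censoring at the last diary assumes that those who stop would have recovered like those still reporting. A sensitivity analysis is there to show what happens if they would have done worse. If many diary-stoppers remain enrolled, 10.3.1 will sit close to the primary result simply because it moved few subjects, and that closeness could be read as robustness that was never tested.

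**Working it through.** **1. The plan's own figure.** 552 / (1 − 0.08) = 600, which reproduces exactly. Expected subjects with incomplete data: 600 × 0.08 = 48 (700 × 0.08 = 56 at the enrolment maximum).

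**2. How many 10.3.1 reaches.** Let f be the share of the 48 who discontinue the study. Then 48f are reassigned and 48(1 − f) stay censored: 48 untested at f = 0, 24 at f = 0.5, none at f = 1. The documents do not give f. This count treats all 48 as unresolved at their last diary. Any who qualify under the last-diary rule are already events, so 48 is an upper limit.

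**3. Three subjects whose diary ends on Day 5.**
- Criteria met at the last diary, no relief medication: responder in both analyses.
- Unresolved and discontinued: censored at Day 5 in the primary, 504 hours in 10.3.1.
- Unresolved and still enrolled: censored at Day 5 in both.

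**4. Illustration of size.** The planning curves are in a figure that is not shown, so the 552 at 90% power cannot be reproduced and the curves below are assumptions:
- log-logistic times rounded up to whole days; placebo median 160, 200 or 240 h; NTZ 40 h shorter; follow-up to 504 h;
- shape tuned so that an unstratified Gehan test with 276 per arm has about 90% power (simulated 91.5%, 89.8% and 89.5%). The resulting differences are 21 to 26 h at the first quartile and 61 to 77 h at the third, the pattern the plan describes;
- 300 per arm, 48 subjects stopping the diary unresolved on Days 2 to 6, 400 runs per row. The Monte Carlo standard error is at most √(0.5 × 0.5 / 400) = 0.025.

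Entries are the probability of a significant result in favour of NTZ. The last column gives 504 h to every unresolved diary-stopper.

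| Placebo median | Loss NTZ vs placebo | f | Primary | 10.3.1 as written | All reassigned |
|---|---|---|---|---|---|
| 200 h | 8% vs 8% | 0.5 | 0.90 | 0.89 | 0.88 |
| 200 h | 10% vs 6% | 0.5 | 0.90 | 0.83 | 0.72 |
| 200 h | 12% vs 4% | 0.5 | 0.89 | 0.74 | 0.53 |
| 200 h | 12% vs 4% | 0 | 0.88 | 0.88 | 0.47 |
| 200 h | 12% vs 4% | 1 | 0.91 | 0.51 | 0.51 |
| 160 h | 12% vs 4% | 0.5 | 0.92 | 0.81 | 0.63 |
| 240 h | 12% vs 4% | 0.5 | 0.89 | 0.67 | 0.43 |

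At f = 0, 10.3.1 is the primary analysis repeated; at f = 1 it is the full stress test. Stopping was simulated as unrelated to later recovery, so the primary column is not biased here. The gap between the last two columns measures how much of the stress test is missing.

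**The case against.** - **Those who stop because they feel well are already events.** This stands in part. The last-diary rule turns many of them into responders, so the point is confined to subjects who do not meet the criteria at their last diary.
- **Diaries are reviewed daily and missing entries are chased.** True, and this should keep the number down. It is a conduct measure, though, and the protocol still allows for 8% incomplete data.
- **The Per Protocol repeat could cover them.** Prolonged diary loss might be classed as a major deviation under Protocol 7.2, but the plan does not say so. Even then the subjects would be removed, not tested against a poor outcome.
- **Discontinuation might be applied broadly.** Protocol 8.4.1 does not say what is discontinued, and neither document defines a completer. A site might record a silent subject as withdrawn. Nothing requires it, and the SAP wording specifies the study.
- **The large effects need strong imbalance.** This stands. The documents give no reason to expect 12% versus 4% in a double-blind trial, and with balanced loss the three analyses nearly agree.
- **The wider rule is harsh.** This also stands. Assigning 504 hours to everyone lost penalises the arm with more loss. It is a stress test, not a better estimate.

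A reader might also infer that 504 hours is not a late enough value because diaries run past Day 21. For response times, the main text does not support this. Response is timed at the start of the 24-hour diary period, and the diary window closes at 11 pm (Protocol 5.10). With first dose at clock hour t, a Day 22 diary gives at most 21 × 24 + 23 − 24 − t = 503 − t hours. A later response is possible only on the Appendix I reading of Day 22 plus 3 days. Cutting the data at 504 hours would not make the assigned value the latest one either, because a subject censored at 504 hours still ranks after an event at that time. The three stated diary ends (Day 21, Day 22, Day 22 plus 3) need reconciling as a separate matter.

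**Conclusion.** The point holds for one defined group: Confirmed Influenza subjects who stop the diary unresolved and stay enrolled. They are censored at the last diary in both the primary analysis and 10.3.1, and no other planned analysis tests them against an unfavourable outcome. Their number lies between 0 and 48 of 600, depending on a split the plan does not state.

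The consequence is small if loss is balanced (0.89 against 0.88) and material only if it is unbalanced (0.74 against 0.53 at 12% versus 4% with f = 0.5; 0.88 against 0.47 if none discontinue). These figures rest on assumed curves, an unstratified test and chosen loss patterns. They show the direction and possible size, not what will happen in this trial.

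A reader might infer that the primary result is biased or the sample size wrong. The documents support neither: no imbalance is known, and 600 follows from 552 and 8%. This is a worthwhile correction to a supportive analysis, not a flaw in the primary one.

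**What to change.** In SAP 10.3.1, replace the discontinuation trigger with: *all Confirmed Influenza subjects without Symptom Response whose last diary assessment is before Day 21, whatever their study disposition*. Align the sensitivity-analysis line in Protocol 8.4.1, or state in the SAP that its definition governs. Subjects counted as responders under the last-diary rule stay as events.

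The cost is one sentence and one programming condition, settled before unblinding as SAP Section 6 requires. The result of this stress test may look less favourable, and it should be labelled as a stress test. The primary analysis and the sample size are untouched. A short table by arm of unresolved subjects whose diary ended early, split by disposition, would be a useful optional addition, since it shows how many subjects the new trigger moves.

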10.3.2 Sensitivity Analysis for a “Per Protocol” Subset

Repeat the primary efficacy analysis for the Per Protocol population.

Analysis Population(s):	Per Protocol
Derived Variables:	See Section 10.2: Primary Efficacy Analysis.

10.4 Secondary Efficacy Analyses

If the primary analysis is significant at the 0.05 level, the secondary efficacy analysis of Time to Ability to Perform All Normal Activities will be formally evaluated at the 0.05 level. If the primary analysis and the secondary efficacy analysis of Time to Return to Normal Activities are both significant at the 0.05 level, the secondary efficacy analysis of Proportions of Subjects Experiencing Complications of Influenza will be formally evaluated at the 0.05 level. If any of these analyses is not significant at the 0.05 level, the subsequent analyses or analysis will be performed as exploratory.

10.4.1 Time to Ability to Perform All Normal Activities

Definitions:

Ability to Perform All Normal Activities

Subject reports a score of 10 on the 0-10 scale for ability to perform normal activities and maintains the score for at least two consecutive daily diary periods without symptom relief medication during or between those two daily diary periods

Time of Ability to Perform All Normal Activities

The time of the first diary entry in which the subject achieves Ability to Perform All Normal Activities

Time to Ability to Perform All Normal Activities

Time (hours) from first dose to the Time of Ability to Perform All Normal Activities

Variables Used for the Analysis

The analysis will require the following variables:

Variable	Source	Format/Notes
Date and time of first medication intake	CRF	
Date and time of completion for each ability assessment record	Subject diary	
Ability to perform normal activities score	Subject diary	The ability to perform normal activities score will be recorded by the subject on a 0-10 scale. In the event that the score was not recorded at a specified time point (e.g., Day 2), the missing data will not be imputed.
Date and time of symptom relief medication intake	Sponsor-provided listing	The list of symptom relief medications will be selected from the listing of all concomitant medications prior to unblinding.

Analysis

The efficacy parameter, Time to Ability to Perform All Normal Activities, will be derived as follows:

Event: Time of Ability to Perform All Normal Activities – time of the first dose
 Censored: Time of last ability assessment – time of the first dose

If Ability to Perform All Normal Activities is achieved at the time of the first ability assessment diary record, the subject will be excluded from the analysis.

If the subject does not achieve Ability to Perform All Normal Activities prior to the subject’s last available diary assessment, but records a “10” for ability to perform all normal activities at the last available diary assessment with no evidence of symptom relief medication intake during that diary period, time of Ability to Perform All Normal Activities will be considered to have occurred at the time of the last available diary assessment.

Time to Ability to Perform All Normal Activities for the NTZ treatment group will be compared to that of the placebo treatment group using a Gehan-Wilcoxon test stratified for (1) time from onset of illness to time of first dose of study medication (0-24, >24-≤36, or >36 hours from onset),, and (2) vaccination status (Y/N). The comparison will be graphically depicted using Kaplan-Meier curves.

Analysis Population(s):	Confirmed Influenza
Derived Variables:	Event: Time of Ability to Perform All Normal Activities – time of the first dose Censored: Time of last ability assessment – time of the first dose

10.4.2 Proportion of Subjects Experiencing Complications of Influenza

Variables Used for the Analysis

The analysis will require the following variables:

Variable	Source	Format/Notes
Complications of influenza	CRF	Investigators will designate an adverse event as a complication of influenza if the event meets protocol-specified criteria

Analysis

Proportions of subjects experiencing one or more complications of influenza will be compared between the treatment groups using a Fisher’s exact test.

Analysis Population(s):	Confirmed Influenza
Derived Variables:	None

